The study population is preschool children attending kindergartens in different districts in Hong Kong. It is planned to recruit around 10 kindergartens. All children attending grade 1 in these kindergarten will be invited to receive a free dental examination and have their decayed primary teeth restored, if possible, in the kindergarten by dentists. Parental informed consent will be obtained before the dental examination and treatment. The planned sample size is 152 children with 396 decayed primary teeth needing restorations. Around half of these teeth, assigned randomly will received SDF treatment around 10 weeks before receiving the restoration. The restored teeth will be re-examined every 6 months for 24 months to assess the treatment outcome. Parents of the study children will be asked to complete a questionnaire at baseline, 6 months and 24 months so as to obtain data on their satisfaction with the aesthetics of their child's teeth and the oral health-related quality of life of the study children.

Background

Dental caries of young children is common in both developing and industrialized countries (Petersen et al., 2016). In Hong Kong, the prevalence of dental caries among 5-year-old children is around 50% (Department of Health, 2013). The adverse effects of dental caries can impact on both children and their families, including significant health, social and economic consequences (Colak et al., 2013).

Previous studies have shown that topical application silver diamine fluoride (SDF) solution is effective in arresting dental caries in young children (Chu et al., 2002; Yee et al., 2009; Zhi et al., 2012; Duangthip et al., 2016). A considerable drawback of SDF application is the black stain on the arrested caries lesions, which may cause dissatisfaction of both children and their parents with aesthetics of the treated teeth (Gao et al., 2016). It was suggested that by applying a saturated solution of potassium iodide (KI) immediately after the application of SDF, would minimize the black stain on the dentin caries lesions (Knight et al., 2006). However, a long term clinical study on elders has shown that the application of KI cannot reduce the blackening of arrested dentine caries lesions from SDF treatment (Li et al., 2016).

Atraumatic restorative treatment (ART), which was first developed in the 1980s, embodies the minimal intervention philosophy of dental caries management. The ART procedures involve removal of soft carious dental tissues using hand instruments and placement of a restoration using adhesive dental material, normally high viscosity glass ionomer cement (GIC) (Holmgren et al., 2013). Clinical evidence shows that ART is a patient-friendly and cost-effective treatment, especially for young children (Tedesco et al., 2016).

Although ART is considered as a satisfactory option for treatment of decayed primary teeth, it may still be difficult to obtain good cooperation from young children during operative procedures. Using SDF application to arrest active dentine caries in the primary teeth of young children may be a more practical management method. When children grow older and become more cooperative, the SDF-arrested caries lesion can then be restored with ART, so as to improve esthetics of the decayed teeth. Furthermore, it is expected that placement of a restoration on an arrested caries lesion is easier and quicker than that on an active caries lesion. The amount of demineralized dental tissues which needs to be removed will also be less, and the bond strengthen between glass ionomer and remineralized dentine may be higher. Thus, it is hypothesized that the success/retention rate of ART restorations placed in decayed teeth which has been treated with topical application of SDF is higher than that of restorations placed in untreated decayed teeth.

In order to find out and compare the outcomes of restoring active dentine caries lesions and those of restoring SDF-treated dentine caries in primary teeth, a well-designed clinical trial is needed. Results of the trial will provide high quality evidence to guide dental clinicians in treating dentine caries in primary teeth of young children.

Objectives

1. To describe the success rate of restorations placed using the atraumatic restorative technique (ART) in untreated dentine caries lesions in primary teeth

2. To describe the success rate of ART restorations placed in dentine caries lesions in primary teeth previously treated by topical application of silver diamine fluoride (SDF) solution
3. To compare the success rate of ART restorations placed in untreated and SDF-treated dentine caries lesions in primary teeth
4. To describe parents' satisfaction with the aesthetics of their child's teeth before and after placement of ART restorations
5. To describe the change in oral health-related quality of life of preschool children before and after placement of ART restorations

Materials and Methods

Study design

This study is a clinical interventional study with two parallel groups. The ICH-GCP principles will be followed.

Study subjects and recruitment

The study population of this proposed study is Hong Kong preschool children attending grade 1 of kindergarten (aged 3-4 years). Around 10 kindergartens in different districts of Hong Kong will be selected. All children attending grade 1 in the selected kindergartens will be invited to join this study. An invitation letter with information on the purpose and procedures of the study will be sent to the parents of the children through the kindergarten. The parents will be asked to give written consent for allowing their child to receive a free oral examination and ART restorations, if indicated for treating the decayed primary teeth in their child's mouth, provided by dentists in the kindergarten. Parental consent will be obtained before inclusion of a child in this study.

Inclusion criteria

Generally healthy children who have at least one decayed primary tooth with a cavity into dentine.

Exclusion criteria

Children with serious systemic diseases/conditions or who are uncooperative during treatment will be excluded. Teeth with signs of pulpal pathology, such as having an abscess or discoloured, will be excluded. Caries lesions which do not have adequate access for hand instruments to prepare the cavity for a filling and those that were treated with SDF solution but with most parts still being active, i.e. easily penetrated by a blunt probe with light force, will also be excluded.

Sample size

Sample size calculation is based on the primary outcome of this study which is the success of ART restorations, defined as restoration present without major defects nor associated active caries. According to a recent systematic review, the two-year survival rate of ART restoration placed in primary teeth is around 70% (Tedesco et al. 2016). It is anticipated that the survival rate of ART restorations placed on arrested caries is slightly higher at 75%. An absolute difference of 10% in the success rate of restorations is regarded as clinically significant. In this non-inferior clinical trial, using one-tailed test with a statistical significance set at 2.5% and a power of 80%, the calculated minimal number of restorations needed in each group is 139 (<http://powerandsamplesize.com/>).

Since more than one caries lesion can be found in a child's mouth, the clustering effect on sample size needs to be considered. Results of the latest oral health survey of Hong Kong 5-year-old children showed that the mean number of untreated decayed primary teeth for children who had dental caries was 4.7 (Department of Health, 2013). In this sample size calculation, it is anticipated that the number of decayed teeth included per study child is 2.5. A design effect of 1.15 is calculated, using an assumed intra-class correlation ρ of 0.1. Thus, the necessary sample size would need to be multiplied by 1.15 and become 160. Furthermore, to compensate for a possible drop-out rate of 15%, the initial sample size is increased to 188 restorations per group. Therefore, 76 children in each group children will be recruited at baseline and the total number of study children will be 152.

Placement of ART restorations

Cavitated caries lesions in the primary teeth of the study children will be restored following the ART procedures (Holmgren et al., 2013). The instruments used are LED illuminated dental mirror, sickle probe, tweezers, hatchet, excavators and flat plastic. The dental restorative material used is a high-strength chemical-cured glass ionomer (Ketac-molar, 3M ESPE, Germany).

The step-by-step ART procedures are briefly described below:

1. isolate the operation site by cotton rolls
2. gain adequate access to the cavity, if necessary a hatchet is used to enlarge the opening of a small cavity
3. excavators of different sizes are used in removing soft carious tissues and preparing the cavity for a filling
4. the cavity is cleaned by water and then dried
5. condition the cavity surface with a weak organic acid, then wash and dry the cavity
6. the glass ionomer material is mixed according to manufacturer's instructions
7. the filling material is placed and pressed into the cavity
8. excess filling material is removed
9. contour and shape of the restoration is modified as necessary and occlusion checked
10. the finished restoration is covered by a layer of varnish or petroleum jelly

Baseline and follow-up data collection

At the baseline, all children with parental consent will be clinically examined in the kindergarten. Disposable dental mirror attached to a handle with an intra-oral LED light and a

ball-ended probe will be used. The status of each tooth will be recorded. Children who have at least one decayed primary tooth with a cavity into dentine will be included into the study. All decayed teeth in the children will be restored, except those with inadequate access and those with signs of pulpal pathology. Around half of these decayed teeth will receive topical application of a SDF solution (Safotide, Toyo Chemical, Japan), through simple random allocation on a child basis using random numbers, around 10 weeks before receiving the restoration. The time used for placement of each restoration will be recorded to the nearest minute.

The children will be examined at 6, 12, 18 and 24 months after placement of ART restorations by calibrated examiners who are not involved in the placement of the restorations. The same instruments used in the baseline examination will be used in the follow-up examinations. The status of the restorations and restored teeth will be assessed and recorded using codes and criteria commonly adopted in previous clinical studies of ART restorations (Lo et al., 2007):

- 0 = restoration present, no caries, no marginal defects or wear
- 1 = restoration present, no active caries, slight defects or wear not greater than 0.5 mm
- 2 = restoration present, marginal defects greater than 0.5 mm
- 3 = restoration present, wear greater than 0.5 mm
- 4 = restoration present, active caries found associated with the filling
- 5 = restoration missing, no active caries, surface hard to gentle probing
- 6 = restoration missing, active caries found, surface soft to probing allowing penetration of the tip of a blunt probe
- 7 = tooth with signs of pulpal pathology
- 8 = tooth missing, extracted due to caries
- 9 = tooth naturally exfoliated

At baseline, information on the children's oral hygiene practice, snacking habit, oral health related quality of life, and parental satisfaction with the appearance of their child's teeth will be collected by a self-completed questionnaire. A validated tool for measuring oral health related quality of life of preschool children in Hong Kong, Chinese version of Early Childhood Oral Health Impact Scale (ECOHIS), will be used (Lee et al., 2009). The same measurement tool will be used at the 6-month and 24-month follow-up.

Primary outcome measure

The primary outcome measure in this clinical study is the success of the ART restorations placed. A restoration is classified as success when it is retained on the tooth without major defects or wear and has no associated active caries (codes 0 and 1). Under this condition, no further treatment is necessary. A restoration is classified as failed when it has major defects (codes 2 and 3), associated active caries (code 4), is missing (codes 5 and 6) or the tooth has signs of pulpal pathology (code 7) or extracted due to caries (code 8). Under these conditions, further treatment may be necessary.

Secondary outcome measures

The secondary outcome measures in this clinical study are the parental satisfaction with aesthetics of their child's teeth and the oral health related quality of life of the child as measured by the ECOHIS before and after placement of ART restorations.

Data analysis

The clinical examination record form and parental questionnaires will first be checked for completeness and obvious errors. Questionnaires with more than 40% of the questions unanswered will be discarded. The collected data will be entered into computer. Data entry and logical errors will be corrected before data analysis.

Basic data analysis will be carried out by using the statistical software SPSS for Windows. Chi-square test and t-test will be performed to assess the comparability between the children in the two study groups regarding their demographic background, oral health related behaviours and baseline dental caries experience. McNemar's test and paired t-test will be used to assess the change in parental satisfaction with aesthetics of their child's teeth and the change in ECOHIS score before and after placement of ART restorations.

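### Follow-up and the primary outcome start at placement of the restoration, so an allocated tooth lost to pulpal pathology or extraction before placement is not counted, although the same events after placement are failures

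*Protocol*

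**What the plan says.** Under Exclusion criteria the protocol states "Teeth with signs of pulpal pathology, such as having an abscess or discoloured, will be excluded", with no time point. The section on baseline and follow-up data collection repeats the rule as a condition for being restored: "All decayed teeth in the children will be restored, except those with inadequate access and those with signs of pulpal pathology".

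The same section assigns SDF "through simple random allocation on a child basis using random numbers, around 10 weeks before receiving the restoration". The interval of about 10 weeks is given only for SDF-treated teeth, there and in the Summary. Neither place says when comparison teeth are restored.

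Follow-up is timed from the restoration: "The children will be examined at 6, 12, 18 and 24 months after placement of ART restorations". Under Primary outcome measure, "The primary outcome measure in this clinical study is the success of the ART restorations placed". That section classes pulpal pathology (code 7) and extraction due to caries (code 8) as failures. No code or rule covers an allocated tooth that is never restored.

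**The concern.** Randomisation makes the two groups of children comparable at allocation. The primary comparison, however, is made among teeth that reach a restoration, and in the SDF arm that point comes about 10 weeks later. Two of the events that can stop a tooth from reaching it are themselves failure events in the primary outcome. The analysed teeth are then survivors of the waiting period, not the teeth that were allocated.

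The Sample size section describes a non-inferiority trial. If the selection favours SDF, it makes non-inferiority easier to declare than the nominal one-sided 2.5% allows. An analysis plan could not fully repair this, because the outcome is defined on restorations placed and the protocol provides no outcome record for a tooth without one.

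**Working it through.** **1. What happens to a tooth.** Take a tooth that is eligible at baseline and abscesses, or is extracted because of caries, some weeks after allocation.

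| Situation | Recorded as |
|---|---|
| Already restored | Code 7 or 8 at the next examination: failed |
| SDF applied, restoration still pending, then not restored | No code; not in the primary outcome |

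**2. The plan's own figure.** Inputs from the Sample size section: success 70% (comparison) and 75% (SDF), difference regarded as clinically significant 10 points (taken as the margin), one-sided 2.5%, power 80%.

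n = (0.70×0.30 + 0.75×0.25) × (1.960 + 0.842)² / (0.05 + 0.10)² = 138.7, so 139 per group, as stated. The design effect is 1 + 1.5×0.1 = 1.15, and 139×1.15 = 159.9, so 160. Then 160/0.85 = 188.2, stated as 188. These figures are not in dispute.

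**3. Size if comparison teeth are restored promptly.** Let f be the share of SDF-arm teeth lost to these events before restoration. The protocol gives no f, so the values below are assumptions. They also assume no such loss in the comparison arm.

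- Gap A: success among restored SDF teeth is 75%, so success among all allocated is 0.75(1−f) and the gap is 0.75f.
- Gap B: success among all allocated SDF teeth is 70%, so restored-only success is 0.70/(1−f).
- Error: success among all allocated SDF teeth is 60%, exactly on the margin. Restored-only success is s = 0.60/(1−f), and the chance of declaring non-inferiority is Φ((s−0.60)/SE − 1.96), with SE = √[(0.70×0.30 + s(1−s))/139]. Clustering is left out.

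| f | All-allocated success (A) | Gap A, points | Restored-only success (B) | Gap B, points | One-sided error |
|---|---|---|---|---|---|
| 1% | 74.3% | 0.75 | 70.7% | 0.7 | 3.2% |
| 2% | 73.5% | 1.5 | 71.4% | 1.4 | 4.1% |
| 3% | 72.8% | 2.25 | 72.2% | 2.2 | 5.1% |
| 5% | 71.3% | 3.75 | 73.7% | 3.7 | 8.1% |

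The planned 5-point advantage would vanish at f = 1 − 0.70/0.75 = 6.7%.

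**4. A rough benchmark for f.** With a constant hazard, 70% success at two years (about 104 weeks) implies 1 − 0.70^(10/104) = 3.4% failing in 10 weeks from all failure codes (2 to 8) together. Pulpal pathology and extraction are two of those seven codes. The benchmark describes restored teeth, and unrestored SDF-treated teeth may differ, but it suggests that 5% is high.

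**5. Size if comparison teeth also wait.** With losses f_S (SDF) and f_C (comparison), and 75% and 70% success among restored teeth, the restored-only difference exceeds the all-allocated difference by 0.75 f_S − 0.70 f_C. With f_S = f_C = 2% this is 1.5 − 1.4 = +0.1 points. With f_S = 1% and f_C = 3% it is 0.75 − 2.1 = −1.35 points, which works against SDF. The sign depends on quantities that the protocol does not give.

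**The case against.** **The question asked.** The objectives concern the success of restorations placed, and a restoration cannot fail before it exists. Timing from placement also gives both arms 24 months of follow-up. This stands as a reason to keep the placement-based analysis. It does not make that analysis a comparison of the groups as randomised.

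**The exclusion may be a baseline screen.** The exception for pulpal pathology sits in the paragraph on the baseline examination, just before allocation is described. This is a fair reading, and no text says that the rule is applied again at placement. However, the exclusion list also contains a rule that can only be applied after SDF ("those that were treated with SDF solution but with most parts still being active"), so the list is not purely a baseline screen. On either reading, an extracted tooth cannot be restored, and the outcome still starts at placement.

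**Direction.** A reader might infer that the plan is simply biased towards SDF. The documents do not support that without a condition, because they do not say when comparison teeth are restored. If those teeth wait untreated, they could be lost at an equal or higher rate.

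**Size.** The loss rate is unknown and may be small over 10 weeks. A reader might take 5% as the expected case, but nothing in the protocol supports it and the benchmark above points lower.

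**Overlap.** The exclusion of SDF-treated lesions that remain mostly active is a more explicit selection after allocation. It is a separate matter: it removes lesions by their response to SDF, whereas this point concerns events that the protocol itself calls failures.

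**Conclusion.** The concern holds with a conditional direction. Because follow-up and outcome start at placement, the restored-only comparison is selected after allocation on an outcome event, and no rule accounts for the teeth lost.

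If comparison teeth are restored promptly, SDF is favoured by about 0.7 to 0.75 points per 1% of its teeth lost. That is about 1.5 points at an assumed 2%, against an anticipated difference of 5 points and a margin of 10, with one-sided error on the margin of about 4% instead of 2.5%. If comparison teeth also wait, neither the size nor the sign can be determined.

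The effect is probably modest and the sample size is not affected. The point should still be settled, because the remedy is cheap and data not recorded at the restoration visit may not be recoverable.

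**What to change.** 1. Under Baseline and follow-up data collection, state when comparison teeth are restored relative to allocation.
2. State that the set of eligible teeth for analysis is fixed at the baseline examination, before allocation. This defines who is counted; whether a given tooth is later restored remains a clinical decision.
3. Record the status of every allocated tooth at the restoration visit, and report unrestored teeth by arm with reasons.
4. Add a pre-specified analysis of all allocated teeth by allocated arm, in which pulpal pathology or extraction due to caries before restoration counts as failure. Assigning these failures to the first follow-up interval leaves the visit schedule and the interval-censored model unchanged. The protocol should also say how this analysis treats teeth left unrestored for other reasons.
5. Report it beside the placement-based analysis, and require the non-inferiority conclusion to be consistent in both.

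Moving the clock to allocation as the only primary analysis is not needed. It would change the stated question and leave the SDF arm's visits offset by about 10 weeks.

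The cost is protocol wording, one code at a visit that already takes place, and one extra analysis. The SDF success rate may look slightly less favourable.

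### Excluding SDF-treated lesions that stay active removes non-responders from the SDF arm only, so the primary comparison is no longer the randomised one

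*Protocol*

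**What the plan says.** The Exclusion criteria section removes, among other lesions, "those that were treated with SDF solution but with most parts still being active", judged by probing. It gives no time point and does not say whether the SDF is the trial's own.

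The Summary describes SDF as the allocated step: "Around half of these teeth, assigned randomly will received SDF treatment around 10 weeks before receiving the restoration". Baseline and follow-up data collection adds that allocation is simple random, by child. The same paragraph says that every decayed tooth is restored apart from two kinds: those without adequate access and those with pulpal pathology. Activity after SDF is not mentioned there.

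Objective 3 is "To compare the success rate of ART restorations placed in untreated and SDF-treated dentine caries lesions in primary teeth". The Sample size section takes 70% two-year success for ART in general and then states: "It is anticipated that the survival rate of ART restorations placed on arrested caries is slightly higher at 75" (per cent). The design is set by "In this non-inferior clinical trial, using one-tailed test with a statistical significance set at 2.5% and a power of 80" (per cent), with 10 points as the clinically significant difference. The outcome codes run from 0 to 9, and none stands for a lesion that was allocated but not restored.

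**The concern.** No passage mentions SDF given before the trial, so the criterion most naturally refers to the SDF that the trial allocates. Read that way, it has three features that together break the protection of randomisation: it acts after allocation, it depends on response to the allocated treatment, and a control lesion can never meet it. No matching rule removes control lesions for being active. Because allocation is by child, a child whose lesions all fail to arrest would drop out of the SDF arm entirely, with no counterpart among controls.

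The Background expects arrested lesions to be easier to restore and says that "the bond strengthen between glass ionomer and remineralized dentine may be higher". On that premise the removed lesions have the worse prognosis and the bias favours SDF. It therefore makes a false claim of non-inferiority more likely, and equally a false claim of superiority, which is what the Background hypothesises.

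A later analysis plan cannot repair this. Follow-up is counted from placement of the restoration and there is no code for an unrestored lesion, so excluded lesions would leave no outcome to analyse.

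**Working it through.** **The plan's own figure.** Inputs from Sample size: 70% and 75% success, margin 10 points, one-sided 2.5%, power 80%.

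- Per group: (0.75×0.25 + 0.70×0.30) × ((1.960 + 0.842)/0.15)² = 138.7, so 139, as stated.
- Design effect: 1 + (2.5 − 1)×0.1 = 1.15, and 139×1.15 = 159.85, so 160.
- Drop-out: 160/0.85 = 188.2, stated as 188. Then 188/2.5 = 75.2, so 76 children per group.

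The figures reproduce. None of the steps allows for lesions lost to the activity criterion.

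**Bias.** Let f be the share of SDF lesions still mostly active, and p_A and p_N the success of arrested and non-arrested lesions if both were restored, with g = p_A − p_N. All allocated lesions would succeed at (1 − f)p_A + f·p_N. The analysed set succeeds at p_A. The difference is f × g.

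The protocol gives neither f nor g. Its only gap is 75% against 70%, or 5 points, and that compares arrested lesions with ART in general, so it is not exactly g. The values of f below (10, 20, 30%) and of g are assumptions.

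**Effect on error.** Unpooled normal approximation. Each arm starts with 76×2.5 = 190 lesions. Effective control number = 190×0.85/1.15 = 140.4; effective SDF number = 140.4×(1 − f).

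- Non-inferiority: true rates 60% (SDF, all allocated) and 70% (control), so SDF is truly at the margin. The analysed SDF rate is 0.60 + f·g, and error = Φ(f·g/SE − 1.960).
- Example, f = 20%, g = 20 points: analysed rate 0.64; SE = √(0.21/140.4 + 0.64×0.36/112.3) = 0.0596; Φ(0.04/0.0596 − 1.960) = 9.9%.
- Superiority: true rates 70% and 70%, analysed SDF rate 0.70 + f·g, false result in favour of SDF.

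| g | Bias (points) at f = 10 / 20 / 30% | Non-inferiority error | Superiority error favouring SDF |
|---|---|---|---|
| 0 | 0 / 0 / 0 | 2.5% throughout | 2.5% throughout |
| 5 points | 0.5 / 1.0 / 1.5 | 3.0 / 3.6 / 4.3% | 3.1 / 3.7 / 4.4% |
| 20 points | 2 / 4 / 6 | 5.3 / 9.9 / 16.3% | 5.5 / 10.5 / 17.8% |

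At g = 10 points the non-inferiority error is 3.7 / 5.2 / 7.0%.

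**Effect on power** (75% against 70%, f = 0 / 10 / 20 / 30%).

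- 190 lesions per arm: 80.5 / 78.5 / 76.0 / 73.0%.
- The Summary's figure ("The planned sample size is 152 children with 396 decayed primary teeth needing restorations") gives 396/2 = 198 per arm: 82.1 / 80.1 / 77.7 / 74.7%. It leaves room for a loss of about 5%, since 198×0.85 = 168.3 and 1 − 160/168.3 = 4.9%.
- If the design effect shrinks with the number of lesions left per SDF child, power at 190 per arm is 78.9 / 77.0 / 74.5% for f = 10 / 20 / 30%.
- The protocol says "it is anticipated that the number of decayed teeth included per study child is 2.5". If that count is already net of this exclusion, there is no power loss.

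**The case against.** The conditioning looks deliberate and is not hidden. The Background describes restoring SDF-arrested lesions, Sample size assumes arrested caries for the 75%, and the primary outcome concerns restorations that were placed. On this view the trial asks a legitimate question about arrested lesions, and the defect is one of labelling. This stands in part: the question is legitimate, but it is conditional on a response to treatment, and the protocol nowhere says that the comparison is then not the randomised one.

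The conflict between sections may be smaller than it looks. The sentence on which teeth are restored sits in the baseline paragraph, ahead of the sentence on allocation, and it also omits the child-level exclusions. That is fair. But its lesion-level exceptions match the Exclusion criteria in every respect except this one, so the two still need reconciling.

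The size is unknown. At the protocol's own 5-point gap the bias is at most 1.5 points for f up to 30%, against a 10-point margin. The larger errors need a gap four times as wide, and removing soft tissue from every restored lesion (step 3 of the ART procedure) gives no support for a gap that large. All of this stands. It limits the evidence for a large effect without excluding one.

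Sensitivity analyses and reporting by arm can properly sit in an analysis plan. The eligibility rule, the follow-up origin and the outcome codes cannot, because they are fixed in this protocol.

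**Conclusion.** The point holds: the rule is wrong as written. Followed on its natural reading, it compares SDF responders with unselected controls and leaves the excluded lesions without an outcome. The issue is validity; the effect on power is modest.

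The size cannot be found from the document. It is zero if prognosis is unrelated to arrest. Over the assumed f of 10 to 30%, the non-inferiority error runs from about 3 to 4% at a 5-point gap to about 5 to 16% at a 20-point gap. The direction, in favour of SDF, rests on the Background's premise that arrested lesions are the better substrate.

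The timing is inferred. If only SDF received before the trial is meant, the rule is an ordinary baseline criterion and the bias disappears, but the text must say so. The correction is needed before the trial collects data, because unrecorded outcomes cannot be recovered afterwards.

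**What to change.** - State whether the criterion refers to trial SDF and when it is applied, and make the Exclusion criteria agree with Baseline and follow-up data collection. Whether still-active lesions are restored is left to the investigators.
- If trial SDF is meant, fix lesion eligibility at the baseline examination, before allocation. Post-SDF activity should not be a reason to leave the randomised analysis set. Analyse each lesion in its allocated group.
- Follow and code every allocated lesion. Add a status for not restored, and take the planned restoration visit as the time origin in both arms.
- If still-active lesions are restored, they enter the primary analysis like any other.
- If they are not restored, their success as restorations stays unobserved. Label the comparison of restored lesions as conditional on arrest and not protected by randomisation, report the number and share excluded by arm, and pre-state sensitivity analyses over a range of assumed success, down to counting none as a success.

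The cost is some wording, one status code and a few more follow-up records. The sensitivity figures for SDF will be less favourable: with s the assumed success of unrestored lesions, the rate is 0.75(1 − f) + s·f. For s = 70%, 50% and 0, this gives 74.5%, 72.5% and 67.5% at f = 10%, and 74%, 70% and 60% at f = 20%. The last value in each set is a bound, not an estimate, since no restoration exists to succeed. If no lesion is left unrestored, these figures do not arise.

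### The design effect of 1.15 assumes equal numbers of restorations per child, which the enrolment and treatment rules exclude; at the plan's own mean and ICC, power is probably a little below the stated 80%

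*Protocol*

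**What the plan says.** The Sample size section starts from two-year success rates of 70% (untreated lesions) and 75% (SDF-treated lesions), a non-inferiority design, one-sided 2.5% significance and 80% power. It states "An absolute difference of 10% in the success rate of restorations is regarded as clinically significant", which serves as the margin, and concludes that "the calculated minimal number of restorations needed in each group is 139".

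For clustering it takes a single anticipated value of 2.5 included teeth per child: "A design effect of 1.15 is calculated, using an assumed intra-class correlation" of 0.1. This raises 139 to 160 restorations per group. A 15% drop-out allowance then gives 188 restorations and 76 children per group, 152 children in all. No SD, CV or distribution of teeth per child is given.

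The rules that settle how many teeth a child contributes are elsewhere. Inclusion criteria admits "Generally healthy children who have at least one decayed primary tooth with a cavity into dentine". Baseline and follow-up data collection says "All decayed teeth in the children will be restored, except those with inadequate access and those with signs of pulpal pathology", and allocates SDF by child. No cap or fixed number of teeth per child is set. The Summary gives the target as 152 children with 396 teeth.

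**The concern.** The formula behind 1.15 takes cluster size as constant. The enrolment and treatment rules make it vary: some children will contribute one restoration and others several. The exclusion of SDF-treated lesions that stay mostly active adds further variation in one group. A constant 2.5 is not even possible, since teeth come in whole numbers.

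Children with many teeth carry more correlated data. At a given mean and ICC, spread in cluster size therefore raises the design effect and reduces the effective sample size. The planned number has almost no reserve to absorb this (188 × 0.85 = 159.8, against a requirement of 160). In a non-inferiority trial the practical consequence is a somewhat higher chance of an inconclusive result than the protocol states.

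**Working it through.** **Inputs from the protocol (Sample size):** success 0.70 and 0.75; margin 0.10; one-sided 0.025; power 0.80; mean m = 2.5 restorations per child; ICC 0.1; drop-out 15%; 76 children per group.

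**Reproducing the plan's figures**

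- Variance term: 0.70 × 0.30 + 0.75 × 0.25 = 0.3975. Distance from the margin: 0.75 − 0.70 + 0.10 = 0.15.
- n = 0.3975 × ((1.960 + 0.842)/0.15)² = 138.7, so 139.
- Design effect: 1 + (2.5 − 1) × 0.1 = 1.15; 139 × 1.15 = 159.85, so 160.
- 160/0.85 = 188.2, given as 188; 188/2.5 = 75.2, so 76 children per group.

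Every figure reproduces, and 1.15 is the equal-cluster formula.

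**Unequal clusters, unweighted**

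DE = 1 + ((1 + CV²) × m − 1) × ICC, where CV is the SD of restorations per child divided by the mean.

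Power = Φ(0.15/√(0.3975/n_eff) − 1.96), with n_eff = n/DE and n = 76 × 2.5 × 0.85 = 161.5 evaluable restorations per group.

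The CV values are assumptions, as the protocol gives none.

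| CV | DE | n_eff | Power |
|---|---|---|---|
| 0 | 1.15 | 140.4 | 80.5% |
| 0.2 (half the children with 2 teeth, half with 3) | 1.16 | 139.2 | 80.2% |
| 0.4 | 1.19 | 135.7 | 79.2% |
| 0.49 (1 + Poisson(1.5)) | 1.21 | 133.5 | 78.5% |
| 0.6 | 1.24 | 130.2 | 77.5% |
| 0.77 (geometric from 1) | 1.30 | 124.2 | 75.5% |
| 0.8 | 1.31 | 123.3 | 75.2% |

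Rounding up to 76 children leaves about half a point in hand. Power drops below 80% once DE exceeds 161.5/138.7 = 1.164, which is a CV of about 0.24. For comparison, an even spread over 1 to 4 teeth (mean 2.5) has a CV of 0.45.

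**Efficient weighting**

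Data analysis plans a two-level model (lesion within child). If it weights children efficiently, DE = mean(m)/E[m/(1 + (m − 1) × 0.1)]:

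- 1 + Poisson(1.5): DE 1.196, power 78.9%.
- Geometric, mean 2.5: DE 1.253, power 77.1%.

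**A higher mean with 152 children**

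- The Summary's 396 teeth are 396/152 = 2.6 per child, or 198 × 0.85 = 168.3 evaluable per group. With efficient weighting, power is 80.2% (1 + Poisson) or 78.2% (geometric).
- Mean 3.0, unweighted: 82.5% at CV 0.6 and 80.2% at CV 0.8.

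**Totals that disagree**

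Sample size implies 2 × 188 = 376 restorations, or 152 × 2.5 = 380. The Summary says 396.

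**The case against.** The strongest reply is that this refines a planning approximation and corrects no wrong sum. The protocol's arithmetic is right for the formula it uses, 2.5 is offered as an anticipated mean, and putting a mean into 1 + (m − 1) × ICC is common practice. That stands as a description. It does not rescue the formula, because the protocol's own rules exclude the zero spread that the formula needs.

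Second, the loss is no larger than the uncertainty in other inputs. With equal clusters, an ICC of 0.05 gives 83.0% and 0.15 gives 78.0%. A success rate of 74% in the SDF group gives 74.4% power, and 76% gives 85.7%. This stands, and it is a reason to report a range. Those inputs may err in either direction, however, whereas ignoring the spread errs only one way.

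Third, the planned analysis is a two-level interval-censored survival model. It may weight children efficiently and use visits before drop-out, so the unweighted 75% is probably too low for it. This also stands.

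A reader might go further in four ways that the documents do not support:

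- **That the trial's power is 75–79%.** The range depends on a CV found nowhere in the protocol.
- **That 160 evaluable restorations per group will not be reached.** On the plan's figures, 76 × 2.5 × 0.85 = 161.5.
- **That power could fall to 73%.** This needs recruitment to stop at 188 restorations per group with 4.7 teeth per child, the survey mean the protocol quotes for 5-year-olds. The protocol sets the number of children at 152.
- **That restoring all eligible teeth itself costs power.** With 152 children, more teeth per child raises power. Only spread around a fixed mean lowers it.

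**Conclusion.** The point holds in conditional form. The design effect of 1.15 is understated, because the number of restorations per child must vary under the protocol's own rules. At mean 2.5, ICC 0.1 and 15% drop-out, 152 children fall short of 80% power by the unweighted formula once the CV exceeds about 0.24. For a CV of 0.4 to 0.8 the unweighted figure runs from about 79% to 75%. With efficient weighting, the two example distributions give about 79% and 77%. The loss is therefore about 1 point at the low end of that range and reaches 3 to 5 points only from a CV of about 0.6, unweighted. It would be partly or wholly offset if the mean were 2.6 or higher. The shortfall is modest and does not threaten the design, but the stated power rests on a premise that the protocol contradicts.

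**What to change.** In the Sample size section:

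1. Replace the design-effect formula with 1 + ((1 + CV²) × m − 1) × ICC.
2. State the assumed mean and SD (or CV) of restorations per child, and the basis for them.
3. Restate the power for 152 children as a range conditional on that CV. With the present inputs and a CV of 0.4 to 0.8, this is 75–79% unweighted. Under the two-level analysis it is roughly 77–79%, taken from the two example distributions.
4. Reconcile the 376 or 380 restorations implied there with the 396 in the Summary.

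This costs a few sentences and a slightly less favourable stated power. Enrolment, design and analysis need not change.
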